18.9. DURATION OF STABLE DISEASE

SD is measured from the start of the treatment until the criteria for disease progression are met, taking as reference the smallest measurements recorded since the treatment started.

18.10. EVALUATION OF BEST OVERALL RESPONSE

The best overall response is the best response recorded from the start of the study treatment until disease progression. The patient's best overall response assignment will depend on the findings of both target and non-target disease and the appearance of new lesions.

Best overall response is defined as the best response across all time points. For example, a patient who has SD at first assessment, PR at second assessment, and PD on last assessment has a best overall response of PR.

18.11. CENTRAL REVIEW

Blinded central review of objective responses will be conducted in order to protect against any reporting bias.

19. APPENDIX B TRANSLATIONAL RESEARCH STUDIES

19.1. INTRODUCTION

A key aim of this study is to evaluate changes in circulating and tumour biomarkers in relation to tumour response. These biomarkers are developing from ongoing whole genome functional RNAi studies in renal cancer model systems and from synthetic lethal mTOR inhibitor and hypoxia RNAi screens conducted within the Francis Crick Institute.

The expression of these putative biomarkers of renal cancer response will be evaluated in tissue donated before and during treatment to define therapeutic response to treatment. In addition, novel techniques (including large scale DNA sequencing and SNP genotyping analyses) will be applied to samples to identify whether germline DNA, genomic tumour DNA, circulating tumour DNA, and circulating microRNAs can guide the identification of patients with disease sensitive to axitinib and provide insight into resistance mechanisms associated with axitinib treatment.

Analysis of tissue for such studies will be performed at the Francis Crick Institute.

19.2. A-PREDICT LABORATORY MANUAL

Detailed instructions for sample collection, processing, labelling, storage and transportation are provided in the A-PREDICT laboratory manual which is available on request from ICR-CTSU and should be referred to in conjunction with this protocol.

19.3. TISSUE ACQUISITION AND PROCESSING AT SITE

19.3.1. BASELINE PRIMARY TUMOUR TISSUE SAMPLE

Image guided percutaneous biopsy of the primary tumour should be performed prior to starting treatment. Five tissue cores from one needle puncture should be obtained; one should be sent for paraffin embedding and analysis by the local pathologist to establish a histological diagnosis. The four remaining cores should be snap frozen in liquid nitrogen within 30 minutes after biopsy and stored at -80°C. The biopsies should be transferred to the Francis Crick Institute on dry ice.

19.3.2. BASELINE BIOPSY OF METASTATIC SITES (OPTIONAL)

Biopsy of a metastatic site at baseline is optional, at the discretion of the treating clinician. As many tissue cores as practicable (maximum of five) from one needle puncture should be obtained. All tissue cores should be snap frozen and stored at -80°C until transfer to the Francis Crick Institute on dry ice.

Selected participating sites in London may be asked to place one of the metastatic biopsy samples into room temperature tubes containing culture medium for transportation to the Francis Crick Institute on the day of collection for the primary culture of malignant and stromal cells. Tubes and culture medium will be supplied by Francis Crick Institute and will be collected by their staff or by tissue collectors employed on the A-PREDICT trial.

19.3.3. PRIMARY TUMOUR TISSUE SAMPLE AT 8 WEEKS

Image guided percutaneous biopsy of the primary tumour should be performed eight weeks after axitinib treatment commenced (day 1 week 9). Five tissue cores should be obtained; one sample will be sent for paraffin embedding and analysis by the local pathologist and the remaining four cores should be snap frozen, stored at -80°C until transfer to the Francis Crick Institute on dry ice.

19.3.4. TUMOUR TISSUE SAMPLE AT PROGRESSION

As many tissue cores as practicable (maximum of five) from one needle puncture should be obtained, preferably from the site of progressive disease, at the time of tumour progression should be snap frozen and stored at -80°C until transfer to the Francis Crick Institute on dry ice. If it is not possible to sample the site of progression, biopsies of the primary tumour tissue should be taken, and processed using the same method as for the baseline and eight week samples.

19.3.5. NEPHRECTOMY SPECIMEN

Nephrectomy specimens if available should be dissected by the local pathologist to obtain sufficient material for routine diagnostic purposes. Following this, separate samples from the tumour and from the remaining normal kidney tissue should be taken for translational research studies. These tissues should be snap frozen in liquid nitrogen within 1 hour after the blood supply to the kidney has been interrupted and stored at -80°C at the local trial centre, until transferred to the Francis Crick Institute on dry ice.

Selected sites may be asked to place a nephrectomy sample into room temperature tubes containing culture medium for transportation to the Francis Crick Institute on the day of collection for primary culture of malignant and stromal cells. Tubes and culture medium will be supplied by Francis Crick Institute and will be collected by their staff or by tissue collectors employed on the A-PREDICT trial.

Trial centres should notify ICR-CTSU one week in advance of any planned surgery - see section 19.4 for details of expedited reporting mechanism.

19.3.6. PALLIATIVE SURGERY SPECIMENS

Tissue specimens from any palliative surgery should be examined by the local pathologist to obtain sufficient material for routine diagnostic purposes. Any additional tissue should be transferred to the Francis Crick Institute for translational research studies. These tissues should be snap frozen in liquid nitrogen immediately and stored at -80°C until transferred to the Francis Crick Institute.

Selected participating sites may be asked to place part of the specimen into room temperature Falcon tubes containing culture medium for transportation to the Francis Crick Institute on the day of collection for primary culture of malignant and stromal cells. Falcon tubes and culture medium will be supplied by Francis Crick Institute and will be collected by their staff or by tissue collectors employed on the A-PREDICT trial.

Trial centres should notify ICR-CTSU one week in advance of any planned surgery - see section 19.4 for details of expedited reporting mechanism.

19.3.7. PARAFFIN EMBEDDED TISSUE SECTIONS

Paraffin embedded core biopsies and nephrectomy specimens that are no longer needed by the local pathologist for diagnostic purposes may be requested and transferred to the Francis Crick Institute as required.

19.3.8. BLOOD AND URINE COLLECTION AND PROCESSING

Venous blood for biomarker analysis will be collected in EDTA tubes. **Two** tubes will be collected on day 1 week 1 prior to starting axitinib treatment, **two** tubes at the day 1 week 9 biopsy, and two at disease progression.

Immediate processing of blood samples must be undertaken locally. Detailed instructions for blood processing are contained in the laboratory manual.

Urine samples will also be collected on day 1 week 1, day 1 week 9, and at disease progression. Samples should be stored at -80°C at trial centres until transfer to Francis Crick Institute.

Each specimen container should be labelled as specified in the laboratory manual. Labels will be supplied by the ICR-CTSU as part of the sample collection kits.

19.3.9. STORAGE AND COLLECTION OF SAMPLES

Blood, urine and tissue samples should be stored at local trial centres in a -80°C freezer and transferred in batches when requested to the Francis Crick Institute on dry ice if not part of the fresh tissue for cell culture study.

19.3.10. TRANSLATIONAL SAMPLE SCHEDULE

Visit/Assessment	Within 21 days prior to registration	Pre-treatment day 1 week 1	Day 1 week 9	Disease progression
Percutaneous image guided biopsy of non-necrotic region of primary renal tumour (5 cores, 1 to be sent to pathology for paraffin embedding, 4 to be snap frozen in liquid nitrogen and stored at -80°C)	X		X	
Percutaneous image guided biopsy of one metastatic site (up to 5 cores to be snap frozen in liquid nitrogen and stored at -80°C) (OPTIONAL).	X			
Percutaneous image guided biopsy of site of progression, or if not possible, of non-necrotic region of primary renal tumour (up to 5 cores to be snap frozen in liquid nitrogen and stored at -80°C)				X
2 EDTA tube blood samples spun down to obtain serum (serum to be stored at -80°C)		X	X	X
Urine sample (1 container to be stored at -80°C)		X	X	X

19.4. SAMPLE TRACKING

Sites will be required to record the collection of participants' samples on an electronic reporting form which will enable tracking of samples by the Francis Crick Institute and ICR-CTSU

19.4.1. TRACKING OF BASELINE SAMPLES FOR INELIGIBLE PATIENTS

In order to minimise invasive procedures, patients will be consented for the trial prior to obtaining both the standard diagnostic biopsy sample and baseline translational study research biopsies. Patients will be asked to provide consent for the research samples to be sent to the Francis Crick Institute should histological examination of the diagnostic sample show that the patient is ineligible for A-PREDICT. Collection of these samples should be notified to the ICR Clinical Trials and Statistics Unit (ICR-CTSU) by telephoning:

[name]

09.00-17.00 (UK time) Monday to Friday

The following information will be required:

- Centre name

Version 9 Dated 02/06/2020

- Confirmation of written informed consent
- Patient's gender
- Patient's date of birth

This notification will allow these samples to be tracked by the Francis Crick Institute and ICR-CTSU.

19.5. EXPEDITED REPORTING OF FRESH TUMOUR TISSUE COLLECTION, PLANNED NEPHRECTOMY OR OTHER PALLIATIVE SURGICAL PROCEDURES

All participating sites must notify ICR-CTSU at least one week in advance of the date of planned nephrectomy or other palliative surgery.

Centres should notify ICR-CTSU of the planned procedures detailed above, by completing the A-PREDICT expedited notification of tissue collection form (included in laboratory manual) and faxing it to:

[name]

For the attention of the A-PREDICT Trial team

19.6. SAMPLE PROCESSING AT THE FRANCIS CRICK INSTITUTE (FORMERLY THE LONDON RESEARCH INSTITUTE)

19.6.1. CORE BIOPSY AND NEPHRECTOMY SPECIMENS

Processing of core biopsy, nephrectomy and surgical specimens will be conducted at the Francis Crick Institute. Microdissection of tumour samples will be performed to separate malignant cells from associated stromal components and RNA and DNA from each will be extracted immediately after dissection according to GLP standards.

All samples will be catalogued in an electronic database at the Francis Crick Institute. The time from core biopsy collection to snap freezing and from ischaemia to snap freezing for nephrectomy specimens will be recorded on a database. All tissues will be stored in an alarmed and locked -80°C freezer which is dedicated to the storage of clinical trial patient samples.

19.7. ANALYSIS OF TUMOUR TISSUES

Tumour tissue analysis aims to correlate changes in biomarkers with toxicity, response to axitinib treatment and survival.

The techniques below may be used to explore this endpoint and are based on the current literature. Equivalent novel methods and technologies might be used at the time of analysis.

19.7.1. RNA AND MIRNA EXPRESSION ANALYSIS

Total RNA from renal specimens will be isolated from tissue obtained before and after Axitinib exposure and at the time of tumour progression. The effects of Axitinib on changes in genome wide and targeted gene expression patterns in malignant cells and tumour stroma will be analysed by RNA expression analysis and the expression patterns of these tissues will be compared between

responding patients, those who achieve disease stabilization and those who progress despite Axitinib treatment.

19.7.2. TUMOUR DNA SEQUENCE AND COPY NUMBER ANALYSIS

Whole genome sequencing of tumour tissue DNA and RNA using deep sequencing technology) will also be conducted. Sequencing will include but not be restricted to regulators of VEGFR, PI3K, mTOR, S6K and VHL pathways including novel regulators of mTOR/S6K pathway signaling identified from functional genomic datasets to identify candidate genes associated with resistance and sensitivity prior to and after axitinib treatment. Tumours will also be profiled for chromosomal numerical heterogeneity status by FISH and for gene copy number variations

19.7.3. DATA ANALYSIS OF GENETIC HIGH-THROUGHPUT METHODS

The data from the high-throughput methods described above will be analysed by the bioinformatics group at the Francis Crick Institute. Pre-treatment expression signatures and changes in expression levels on treatment will be correlated with clinical response, primary resistance and to the development of secondary resistance to axitinib treatment as assessed by CT scanning. Gene specific quantitative rtPCR analyses will be used to validate expression data from the high-throughput assays and to correlate findings from whole genome RNAi analyses performed in renal cancer models *in vitro*.

19.7.4. TUMOUR IMMUNOHISTOCHEMISTRY AND IN SITU HYBRIDIZATION

Molecular analyses of any additional paraffin embedded tissue sections may be carried out to determine the effects of axitinib on changes in the phosphorylation status of proteins in the mTOR signalling pathway in tumour tissue (to include PTEN, p-AKT, p-PRAS40, p-70S6K, p-S6RP, p-4E-BP1) and to determine the effects of axitinib on changes in the levels of target genes and proteins in the VHL-HIF pathway in tumour tissue (to include VHL, HIF, VEGF family, GLUT-1). Additional pathways may be evaluated based on the contemporary literature at the time of analysis.

19.8. ANALYSIS OF BLOOD SAMPLES

One blood sample (taken at baseline) will be analysed for genomic DNA, and two blood samples taken at day 1 week 1, day 1 week 8 and disease progression will be analysed for circulating biomarkers, including circulating angiogenic markers, microRNA and tumour DNA.

Plasma levels of VEGF, PIGF, sVEGFR1-3 and new regulators of angiogenesis will be measured by ELISA analysis of plasma samples collected immediately before starting axitinib and on treatment. High-throughput deep-proteome analysis will be used to identify new protein biomarkers that predict axitinib sensitivity and resistance.

Total RNA from human blood will be isolated before and after axitinib exposure and RNA concentration will be quantified. Differential miRNA expression will be analysed and results will be compared with miRNA expression in matched tumour samples and data analysed in the Bioinformatics department at the Francis Crick Institute.

Circulating tumour DNA will be quantified to analyse tumour dynamics during axitinib treatment. Circulating cell-free DNA will be isolated from plasma samples after double centrifugation to remove any cellular components and debris and the amount of circulating DNA of mutated genes that were identified in the tumour DNA sequencing project will be quantified by real time PCR analysis and BEAM or by Solexa (Illumina, San Diego, USA) high throughput sequencing techniques.

Isolation and analysis of genomic DNA in parallel with tumour DNA will be important to validate tumour specific genomic copy number changes. Genomic DNA will be isolated by standard protocols from white blood cells that were extracted from peripheral blood by centrifugation.

The specific techniques which will be utilised are based on the current literature, but equivalent novel methods and technologies might be used at the time of analysis.

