- Symptom assessment (NCI CTCAE v.4)
- Serum Thyroid Function Tests (Free T4 and TSH)
- Assessment of concomitant medications

NB. If the participant has any axitinib treatment interruptions \geq 1 week, please contact the trials office for advice on scheduling of subsequent follow up and research biopsy.

7.4. DAY 1 WEEK 5:

The following investigations should be conducted on day 1 of week 5 (+/- 72 hrs):

- Physical examination including ECOG performance status, body weight, temperature, blood pressure, heart rate, respiratory rate
- Haematology, coagulation, glucose, renal and liver function, serum calcium and LDH
- Urinalysis for protein
- Symptom assessment (NCI CTCAE v.4)
- Assessment of compliance with study medication
- Serum Thyroid Function Tests (Free T4 and TSH)
- Assessment of concomitant medications

NB. If the participant has any axitinib treatment interruptions \geq 1 week, please contact the trials office for advice on scheduling of subsequent follow up and research biopsy.

Dispense axitinib to patient (see section 8)

7.5. DAY 1 WEEK 8

Patient should be instructed to stop axitinib 5-7 days prior to biopsy (after 7 weeks of treatment)

NB. If the participant has any axitinib treatment interruptions \geq 1 week, please contact the trials office for advice on scheduling of subsequent follow up and research biopsy.

7.6. DAY 1 WEEK 9

The following investigations/assessments should be conducted on day 1 week 9 (+/- 72 hrs):

- Physical examination including ECOG performance status, body weight, temperature, blood pressure, heart rate, respiratory rate
- Haematology, coagulation, glucose, renal and liver function, serum calcium and LDH
- Urinalysis for protein
- Symptom assessment (NCI CTCAE v.4)
- Blood samples and urine sample for biomarker analysis (see Appendix B)
- CT thorax, abdomen and pelvis and assessment of response according to RECIST 1.1 criteria.
- Percutaneous biopsy of non-necrotic region of primary renal tumour (from same site as first biopsy if possible) via appropriate (US or CT) guidance (see Appendix B)
- Assessment of compliance with study medication (see section 8)
- Assessment of concomitant medications

Dispense axitinib, with instructions to patient to start 2-3 days after biopsy (see section 8)

NB: CT thorax, abdomen and pelvis should be carried out prior to biopsy

7.7. DAY 1 WEEK 13 (AND EVERY 4 WEEKS TO SIX YEARS/DISEASE PROGRESSION):

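### Section 19.8 describes the follow-up biomarker blood as on treatment and dates it to week 8, but the schedule draws it at the week 9 biopsy after about 5-7 days off axitinib; serum and plasma are also confused

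*Combined protocol and SAP*

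**What the plan says.** **Analysis (19.8).** Circulating markers are to be measured in "two blood samples taken at day 1 week 1, day 1 week 8 and disease progression". The angiogenic markers come from "ELISA analysis of plasma samples collected immediately before starting axitinib and on treatment". Cell-free DNA is also taken from plasma, and genomic DNA from white blood cells in a baseline sample.

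**Collection (19.3.8).** Two tubes are drawn before the first dose, then two "tubes at the day 1 week 9 biopsy, and two at disease progression". The Trial Summary, section 7.6, the schedule of assessments (7.13) and the translational sample schedule (19.3.10) agree on week 9.

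**Drug status.** The week 8 entry (7.5) reads: "Patient should be instructed to stop axitinib 5-7 days prior to biopsy (after 7 weeks of treatment"). Sections 7.13 and 8.1 also give 5-7 days; the Trial Summary and section 3 say one week. Axitinib restarts 2-3 days after the biopsy (7.6, 8.1).

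**Material.** Section 19.3.8 says "Venous blood for biomarker analysis will be collected in EDTA tubes". The schedule in 19.3.10 lists "2 EDTA tube blood samples spun down to obtain serum (serum to be stored at -80°C") and names no other blood fraction.

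**The concern.** Biomarker change as a consequence of axitinib is a stated exploratory endpoint (4.3), and Appendix B (19.1) calls the evaluation of biomarker changes in relation to tumour response a key aim. For a circulating marker, the estimate that an analyst following 19.8 would report is change from pre-dose to on treatment. The sample actually scheduled is taken in a planned gap in dosing. If a marker moves back towards its starting level once drug is withdrawn, the week 9 difference understates the on-drug change. A null result could then be read as no effect of axitinib when it reflects recovery. Nothing in 19.8 or 10.2.3 tells the analyst that the drug was interrupted, or asks for time since last dose to be taken into account.

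The second matter is what is kept. If a site followed 19.3.10 to the letter, the schedule would not provide for the plasma or the cells on which 19.8 depends.

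**Working it through.** No sample size or error rate is at issue. The check is visit-day arithmetic and a side-by-side reading.

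**Visit days.** Day 1 of week w falls on study day 7(w − 1) + 1.
- Day 1 week 8: 7 × 7 + 1 = day 50.
- Day 1 week 9: 7 × 8 + 1 = day 57.
- Difference: 57 − 50 = 7 days.

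**Time off drug at the scheduled draw.** Stopping 5-7 days before a day 57 biopsy puts the stop at 57 − 7 = day 50 to 57 − 5 = day 52. The draw at that biopsy is therefore 5-7 days after the stop.

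**Effect of the visit window.** Section 7.6 allows ±72 hours, so the visit may fall on days 54 to 60. If the stop is fixed at day 50 and the visit moves, the gap is 54 − 50 = 4 days to 60 − 50 = 10 days. If the stop is counted back from the actual biopsy date, it stays at 5-7 days. Time off drug can thus differ between patients.

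**A draw at week 8, as 19.8 states.** Day 50 is at the stop or up to two days before it (stop on days 50-52). That would be a different sample from the scheduled one. No biomarker blood is listed for that visit in 7.5 or 7.13.

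**Side by side.**

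| Item | Section 19.8 | Collection text |
|---|---|---|
| Second draw | Day 1 week 8 | Day 1 week 9 (Trial Summary, 7.6, 7.13, 19.3.8, 19.3.10) |
| Drug status | On treatment | About 5-7 days after stopping, before restart (7.5, 7.6, 7.13, 8.1) |
| Fraction | Plasma (ELISA, cell-free DNA); white cells (genomic DNA) | Serum (19.3.10) |

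**Reading the three rows.** Section 19.3.3 equates eight weeks after the start of treatment with day 1 week 9, so week 8 in 19.8 is probably a slip for eight weeks. Correcting it that way settles the first row and confirms the second: the blood is drawn off drug. The third row stands on its own.

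**The case against.** The strongest reply is that the pause is deliberate and openly stated, and that drawing blood at the biopsy visit gives time-matched specimens, which 19.8 uses when it compares blood miRNA with matched tumour. On treatment also looks like a loose label: section 1.6 applies it to the biopsies, which are taken in the same pause, and 19.8 speaks of before and after exposure for blood RNA. Sites cannot be misled about when to draw, because all the collection instructions agree. The biomarker sub-group analyses are descriptive and hypothesis-generating (10.2.3). Compliance is already assessed at week 9.

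Much of this stands. It shows that the week 9 draw is intended and can be kept. It does not make the label accurate, and it does not tell whoever analyses the data that dosing had stopped. The tablet count in 8.13 does not by itself give the date and time of the last dose.

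Four stronger readings are tempting, and the documents do not support them:
- *The week 8 wording causes the off-drug sampling.* It does not. The off-drug draw follows from the planned biopsy pause; 19.8 merely mislabels it.
- *Week 8 day 1 is the last day on drug.* The documents do not say so; the stop may fall on any of days 50 to 52.
- *The tube counts contradict each other, because 19.8 mentions one baseline sample and then two.* The one sample for genomic DNA can be one of the two baseline EDTA tubes, with its cells used for DNA and its plasma for markers.
- *The genomic DNA comparison is impossible.* Sections 19.2 and 19.3.8 place detailed processing in the laboratory manual, which is not among the documents and may specify plasma and cells. Section 19.3.9 also refers generally to stored blood. Serum from EDTA tubes may simply be a slip for plasma.

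**Conclusion.** The point holds as a labelling and consistency fault with a real consequence for interpretation. As written, off-drug week 9 blood would be presented as on-treatment change. This rests on the collection schedule governing, which all five collection passages support, and on the stop rule being followed.

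The time off drug is about 5-7 days, or 4-10 days if the stop is fixed at day 50 and the full visit window is used. How much of an on-drug change would be lost over that time is unknown. The documents give no recovery time for any marker, and assumed half-times could produce almost any answer, so no figure is offered.

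The serum and plasma conflict is plain in the protocol text; whether it affected stored material depends on the laboratory manual. The consequence is confined to the exploratory biomarker endpoints. The primary endpoint, sample size and stopping rule are untouched. This is a minor point, worth correcting because correction is cheap.

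**What to change.** 1. In 19.8, change day 1 week 8 to day 1 week 9, to match the collection schedule.
2. Record the date and time of the last axitinib dose with each biomarker sample.
3. Describe, analyse and report the week 9 blood as taken after a treatment interruption, not as on treatment, and summarise the time since last dose alongside the results.
4. In 19.3.10, replace serum with the plasma and cell fractions that 19.8 needs, and state that genomic DNA comes from the cells of a baseline EDTA tube. Check this against the laboratory manual.
5. Reconcile the two descriptions of the pause (5-7 days in 7.5, 7.13 and 8.1; one week in the Trial Summary and section 3), so that the reported interval has one source.

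The cost is wording and one eCRF field. No visit, sample or treatment rule needs to change. If week 9 sampling is already complete, the label can still be corrected and the fractions actually stored can be documented before reporting. The last dose can be taken from source records where they hold it.
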